# 10.1 EVALUATION DURING TREATMENT/INTERVENTION

	Any time prior to start	≤4 weeks prior to start	≤2 weeks prior to start	Cycle 1 				Cycle 2 and onwards 				End of treatment visit 
Week #				1	2	3	4	1	2	3	4	
Histological confirmation of diagnosis	X											
Informed consent		Х										
History, concomitant medications and toxicity			X	X	Х	X		X				Х

assessment											
Physical exam, vital signs  , and performance status		X	x	X	x		X			X	
Complete blood count, comprehensive metabolic panel 		X	X	X	X		Х			X	
PT/PTT		Х									
ECG 	X										
Serum Pregnancy Test 		X									
Radiographic tumor assessment 	X								X		
Nintedanib pill diary/compliance review			X				x			X	
Nintedanib dosing		Nintedanib 200mg Twice Daily, Every Day									

- 1. Each treatment cycle consists of 28 days and will be repeated until tumor progression (PD according to RECIST version 1.1) confirmed by tumor imaging.
- 2. Beginning with Cycle 2, each cycle start date will coincide with the physician visit date.
- 3. End of treatment (EOT) visit: within 14 days after permanent termination of trial drug(s). If permanent discontinuation of study drugs falls on a scheduled visit, examinations as defined for EOT should be preformed instead of the examination of the scheduled visit.
- 4. Vital signs: includes respiratory rate, pulse, temperature and blood pressure.
- 5. Comprehensive metabolic panel (CMP) includes: BUN, creatinine, ALT, AST, albumin, glucose, total protein, calcium, bilirubin, bicarbonate, sodium, chloride, potassium, alkaline phosphatase.
- 6. 12-Lead resting electrocardiogram (ECG) will be performed at screening
- 7. For women of childbearing potential

#### **Evaluations during treatment**

Please note, because of the potential need for blood tests, CT/MRI scan, and physician visit scheduling to vary (due to both physician and patient issues), to avoid violation of, and deviation from the protocol, blood tests, CT/MRI scans, and physician visits (including physical exam, vitals, blood pressure, performance status, and concomitant medications) may vary by up to one to week (7 days) before and 1 week (7days) after the scheduled date. The study treatment will not be interrupted, with the next cycle beginning before the patient is evaluated for toxicity.

- History, concomitant medications and toxicity assessment, physical exam, vital signs, and performance status assessment on Week 1, Week 2, Week 3 of Cycle 1, then on Week 1 of Cycle 2, and each cycle thereafter.
- Complete blood count, comprehensive metabolic panel on Week 1, Week 2, Week 3 of Cycle 1, then on Week 1 of each cycle thereafter.
- Nintedanib diary to be collected on Week 1 of each new cycle.
- A repeat CT or MRI of evaluable or measurable disease at baseline, then at eight weeks, and then every eight weeks thereafter. CT or MRI may be performed more frequently if determined necessary per investigator discretion. The same imaging modality performed at baseline (CT or MRI) will be repeated at subsequent imaging

#### **Evaluations at End of Treatment visit**

- History, concomitant medications and toxicity assessment.
- Physical exam, vital signs, and performance status assessment.
- Nintedanib diary to be collected.
- Complete blood count, comprehensive metabolic panel.
- Unused study medication to be returned to MSKCC pharmacy.

#### **Correlative studies**

Exploratory biomarker analysis will be performed on archival tissue or any new tissue procurement that becomes clinically available (i.e. no additional biopsy will be procured for the purpose of these studies.)

We will define the frequency and predictive impact of FGFR overexpression and amplification in patients with treatment refractory esophagogastric cancer enrolled on this

study. Protein expression of FGFR1, 2, 3 will be assessed by immunohistochemistry and measured. FGFR genomic alterations and amplification will be assessed by massively parallel sequencing using the IMPACT assay and proteomics-based CEER assay. We will also compare the mutational status of archival tumor samples collected for clinical purposes.

Patients with available tumor tissue will be separately consented for protocol 12-245, "Tumor Genomic Profiling in Patients Evaluated for Targeted Cancer Therapy."

# 11.1 TOXICITIES/SIDE EFFECTS

For definition of dose limiting toxicity and suggested medical management of Nintedanib associated toxicities refer to Section 9.1 and 9.2.

Nintedanib (Nindetanib)

Nintedanib has shown an acceptable safety profile, on the basis of results from the phase I and phase II studies conducted to date. The most commonly reported treatment-emergent adverse events (TEAEs) were GI disorders including nausea, vomiting, diarrhea, and AST/ALT/bilirubin elevations. Below is a list of TEAEs based on their likelihood of occurrence at a dose of ≤200mg BID:

Likely: (>7% incidence all grades)

- Diarrhea
- Nausea
- Vomiting
- Decreased appetite
- Fatigue
- Asthenia
- Weight loss
- Abdominal pain
- Aspartate aminotransferase elevation
- Alanine aminotransferase elevation
- Gamma-glutamyltransferase elevation
- Hyperkalemia
- Hyponatremia

#### Less Likely (≤5% all grades)

- Abdominal pain
- Constipation
- Headache
- Hypertension
- Alkaline phosphatase elevation

Special warning and precautions for use:

During treatment with Nintedanib, all study patients will be advised to avoid sun exposure or artificial UVA/UVB radiation in solaria or tanning booths. If exposure to sunlight cannot be avoided, protective clothing and broad spectrum (UVA/UVB) sunscreens should be used. After discontinuation of Nintedanib treatment all protective measures should be continued for at least 2 weeks

## **11.1 Definitions of Adverse Events**

#### Adverse Event

An adverse event (AE) shall mean any untoward medical occurrence, including an exacerbation of a pre-existing condition, in a patient or clinical investigation subject administered a pharmaceutical product. The medical occurrence does not necessarily have a causal relationship with the treatment.

#### Serious Adverse Event

A serious adverse event (SAE) is defined as any AE which results in death, is immediately life-threatening, results in persistent or significant disability/incapacity, requires or prolongs patient hospitalization, is a congenital anomaly/birth defect; or based upon appropriate medical judgment, may jeopardize the patient and may require medical or surgical intervention to prevent one of the other outcomes listed in the above definitions.

#### Severity of adverse event

The severity of adverse event should be classified and recorded according to the Common Terminology Criteria for Adverse Events (CTCAE) Version 4.0

#### Causal relationship of adverse event

Medical judgment should be used to determine the relationship, considering all relevant factors, including pattern of reaction, temporal relationship, de-challenge or re-challenge, confounding factors such as concomitant medications, concomitant diseases, and relevant history. Assessment of causal relationship must be recorded for each adverse event.

Causality will be reported as either "Yes" or "No."

- Yes: There is a reasonable causal relationship between the investigational product administered and the AE
- No: There is no causal relationship between the investigational product administered and the AE

#### 11.2 Malignant disease progression

Expected fluctuations or expected deterioration of the underlying disease should not be recorded as an AE unless at least one of the following criteria is me:

- The worsening of the disease constitutes an SAE
- Additional treatment is required, i.e., concomitant medication is added or changed
- An unexpected deterioration from baseline has occurred in the opinion of the investigator

# 11.3 Worsening of pre-existing conditions

A pre-existing condition present at baseline, which remains unchanged during the trial, does not need to be recorded as adverse event. Any worsening of any pre-existing baseline condition should be recorded as an adverse event. Examples of worsening of a pre-existing condition that should be recorded as an AE are given below:

- Worsening of condition meets the criteria for an SAE
- Action is taken with the investigational drug (i.e. dose is reduced of treatment is discontinued)
- Treatment is required (concomitant medication is added or changed)
- The investigator believes a patient has shown a clear deterioration from baseline symptoms

# **11.4** Documentation and Reporting of adverse events

All adverse events occurring after the subject has signed the informed consent must be fully recorded in the subject's case record form.

Each serious adverse event (SAE) must be followed up until resolution or stabilization by submission of updated reports to the designated person. An isolated laboratory abnormality that is assigned grade 4, according to CTC definition, is not reportable as an SAE, unless the investigator assesses that the even meets the standard ICH criteria for an SAE. CTC grade 4 baseline laboratory abnormalities that are part of the disease profile should not be reported as an SAE, specifically when they are allowed or not excluded by the protocol inclusion/exclusion criteria.

When required, and according to local law and regulations, serious adverse events must be reported to the Ethics Committee and Regulatory Authorities.

# 12.0 CRITERIA FOR THERAPEUTIC RESPONSE/OUTCOME ASSESSMENT

All patients who receive at least one week of Nintedanib will be evaluable for toxicity and response. Patients who are unable to complete one week of therapy will not be evaluated for toxicity or response and will be replaced by a new patient.

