#### Secondary objectives:

- 1) To evaluate the objective response rate, defined as both complete response (CR) and partial response (PR), as measured by RECIST response criteria.
- 2) To evaluate the tolerability and incidence adverse event profile of Nintedanib in this patient population.
- 3) To perform an exploratory correlative analysis assessing the relationship of FGFR amplification and overexpression with progression free survival and response.

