# 12.3 Evaluation of objective response rate

The secondary endpoints include objective response rate, safety and tolerability. The objective response rate will be the best overall response, or the best response recorded from the start of treatment until disease progression/recurrence. The patient's best response assignment will depend on the achievement of both measurement and confirmation criteria by RECIST and defined as complete response (CR), and partial response (PR).

The type, frequency, severity, timing, and relationship of each adverse event will be determined as per the NCI Common Toxicity Criteria, version 3.0. Given the small sample size, the analysis of correlative biomarkers will be exploratory and hypothesis generating.

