# 14.0 BIOSTATISTICS

This is a single institution, open-label, non-randomized, single-arm phase II evaluation. The primary objective of this study is to determine the 6 month progression free survival (PFS) for patients with advanced or recurrent EG cancer treated with Nintedanib 200 mg twice per day. PFS is defined in Section 12.2.

We are using 6 month PFS as the primary endpoint in this study of 2nd line treatment for advanced EG cancer. Previous studies have estimated the 6 months to be 4.5% with placebo, 12% with everolimus and 18% for ramucirumab. Based on this information, a 6 month PFS of 10% or less will be considered unacceptable while 28% or more will be considered promising. Using an exact binomial single stage design we require 32 patients to differentiate between 6-month PFS of 10% and 28% with type I and II error rates of 10% each. If 6 or more patients are alive and progression free at 6 months, the regimen is declared promising. With a total of 32 patients, we also have 89% power to detect an improvement in the response rate from 5% to 20% with a one-sided type I error rate of 10%. We assume an accrual rate of 1-2 patients per month for study duration of 18-35 months.

Secondary endpoints involve an assessment of the overall response rate (complete and partial responses), as determined by RECIST criteria. Toxicities will also be assessed and tabulated. Correlative analyses will be exploratory in nature. We will assess the relationship between FGFR amplification (by FISH) and FGFR overexpression (by IHC) with progression free survival using log-rank test. Fisher's exact test will be employed to assess these relationships with response.

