#### 16.3 Data and Safety Monitoring

The Data and Safety Monitoring (DSM) Plans at Memorial Sloan-Kettering Cancer Center were approved by the National Cancer Institute in September 2001. The plans address the new policies set forth by the NCI in the document entitled, "Policy of the National Cancer Institute for Data and Safety Monitoring of Clinical Trials" which can be found at: http://cancertrials.nci.nih.gov/researchers/dsm/index.html. The DSM Plans at MSKCC were established and are monitored by the Office of Clinical Research. The MSKCC Data and

Safety Monitoring Plans can be found on the MKSCC Intranet at: http://mskweb2.mkscc.org/irb/index.htm

There are several different mechanisms by which clinical trials are monitored for data, safety, and quality. There are institutional processes in place for quality assurance (e.g., protocol monitoring, compliance and data verification audits, therapeutic response, and staff education on clinical research QA) and departmental procedures for quality control, plus there are two institutional committees that are responsible for monitoring the activities of our clinical trials programs. The committees: Data and Safety Monitoring Committee (DSMC) for Phase I and II clinical trials, and the Data and Safety Monitoring Board (DSMB) for Phase III clinical trials, report to the Center's Research Council and Institutional Review Board.

During the protocol development and review process, each protocol will be assessed for level of risk and degree of monitoring required. Every type of protocol (e.g., NIH sponsored, in-house sponsored, industrial sponsored, NCI cooperative group, etc.) will be addressed and the monitoring procedures will be established at the time of protocol activation.

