# 17.3 Serious Adverse Event (SAE) Reporting

Any SAE must be reported to the IRB/PB as soon as possible but no later than 5 calendar days. The IRB/PB requires a Clinical Research Database (CRDB) SAE report be submitted electronically to the SAE Office at [contact]. The report should contain the following information:

Fields populated from CRDB:

- Subject's name (generate the report with only initials if it will be sent outside of MSKCC)
- Medical record number
- Disease/histology (if applicable)
- Protocol number and title

Data needing to be entered:

- The date the adverse event occurred
- The adverse event
- Relationship of the adverse event to the treatment (drug, device, or intervention)
- If the AE was expected
- The severity of the AE
- The intervention
- Detailed text that includes the following
  - An explanation of how the AE was handled.
  - A description of the subject's condition.
  - Indication if the subject remains on the study.
  - o If an amendment will need to be made to the protocol and/or consent form.

The PI's signature and the date it was signed are required on the completed report.

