# 17.3.1 Adverse event and serious adverse event reporting

Upon inclusion into a trial, the patient's condition is assessed (e.g. documentation of history/concomitant diagnoses and diseases), and relevant changes from baseline are noted subsequently.

All adverse events, serious and non-serious, occurring during the course of the clinical trial (i.e., from signing the informed consent onwards through the trial follow-up period of 28 days following the last administration of the drug) will be collected, documented and reported by the investigator. For each adverse event, the investigator will provide the onset date, end date, intensity, treatment required, outcome, seriousness, and action taken with the investigational drug. The investigator will determine the relationship and expectedness with the investigational drug to all AEs as defined in the listed adverse event section of Boehringer Ingelheim's Investigator Brochure for the product.

If not stipulated differently in the pharmacovigilance agreement, SAEs are to be reported to BI using the BI IIS Serious Adverse Event Report Form including a documented causal relationship assessment and providing as much detail regarding the SAE as possible. With receipt of follow-up information, all remaining fields on the SAE form are to be completed or updated.

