# Drug-induced liver injury (DILI)

Drug-induced liver injury is under constant surveillance by BI and regulators and is considered a protocol-specified adverse event of special interest (AESI). Timely detection, evaluation, and follow-up of laboratory alterations of selected liver laboratory parameters to distinguish an effect of the investigational drug from other causes are important for patient safety and for the medical and scientific interpretation of the finding.

The following are considered as protocol-specified AESI:

• An elevation of ALT and / or AST > 5x ULN without bilirubin elevation measured in the same blood draw sample

• An elevation of AST and/or ALT >2.5 fold ULN combined with an elevation of bilirubin to >1.5 fold ULN measured in the same blood draw sample

Patients showing above laboratory abnormalities need to be followed up until the protocol specific retreatment criteria have been met and according to **Appendix II** of this clinical trial protocol.

Protocol-specified AESI are to be reported in an expedited manner similar to Serious Adverse Events, even if they do not meet any of the seriousness criteria.

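### Section 12.0 removes from the toxicity evaluation, and replaces, patients who cannot complete one week of Nintedanib, even when toxicity is the reason

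*Combined protocol and SAP*

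**What the plan says.** Tolerability is the second of the secondary objectives: "To evaluate the tolerability and incidence adverse event profile of Nintedanib in this patient population".

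Section 12.0 then defines who is evaluable. Patients with at least one week of drug count for both toxicity and response. For the rest, "Patients who are unable to complete one week of therapy will not be evaluated for toxicity or response and will be replaced". The rule does not distinguish reasons for stopping.

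Section 14.0 plans the analysis in one sentence, "Toxicities will also be assessed and tabulated", and names no denominator. Section 12.0 is the only place that defines a set of patients for toxicity.

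Other sections are wider. Section 12.3 says "The type, frequency, severity, timing, and relationship of each adverse event will be determined". Section 11.4 requires every adverse event after consent to be entered in the case record form. Section 17.3.1 sets the collection period as "from signing the informed consent onwards through the trial follow-up period of 28 days following the last administration of the drug". None of these has a one-week exception.

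**The concern.** A minimum-exposure rule with replacement can be argued for when the question is response. It does not suit tolerability, because inability to stay on the drug for a week may itself be the outcome of interest. If the reason for leaving is toxicity, the rule removes exactly the patients who tolerated the drug worst and puts others in their place.

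The protocol also disagrees with itself. Sections 11.4, 12.3 and 17.3.1 collect and describe all adverse events, while Section 12.0 bars some of the same patients from the evaluation. An analyst who follows Section 12.0 as written would leave out events already in the database. With about 32 patients, one or two of them move a reported rate by several percentage points.

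**Working it through.** **The plan's own figures.** The plan gives no first-week discontinuation rate and no expected rate of serious toxicity, so there is no plan figure on this point to reproduce. The Section 14.0 design, which the fix should leave alone, does reproduce. With X binomial (32, p), P(X ≥ 6) = 0.094 at p = 0.10 and 0.919 at p = 0.28, so both errors are within the stated 10%.

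**Step 1: who is lost.** Section 12.0 excludes patients unable to complete a week of therapy. That is narrower than everyone who stops in week 1. For severe diarrhea (Section 9.4.1) and for vomiting or nausea (Section 9.4.3), the drug is held until recovery and resumed at a lower dose. Section 9.3 takes a patient off protocol only at a delay of 21 or more consecutive days. A patient held on day 4 who later resumes can still reach a week of drug. The patients lost are mainly those who die or permanently discontinue in week 1.

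**Step 2: effect on the reported rate.** Let x be the patients with a given serious toxicity among the 32 evaluable, k the patients replaced, and t the number of those k who had the toxicity. The table shows x/32; the rate in all treated patients is (x + t)/(32 + k). The table is too low whenever t/k exceeds x/32. Intervals are exact (Clopper-Pearson) 95%; x, k and t are assumed.

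| Case | Rate | 95% CI |
|---|---|---|
| Table as planned, x = 3 | 3/32 = 9.4% | 2.0 to 25.0 |
| k = 1, t = 1 | 4/33 = 12.1% | 3.4 to 28.2 |
| k = 2, t = 2 | 5/34 = 14.7% | 5.0 to 31.1 |
| k = 2, t = 0 | 3/34 = 8.8% | not computed |

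The differences are 12.1 − 9.4 = 2.7 and 14.7 − 9.4 = 5.3 percentage points. The last row shows that counting all treated patients does not always raise the rate: if early stopping is unrelated to toxicity, it lowers it slightly. For an event otherwise unseen, the table would show 0/32 where the truth is 1/33 = 3.0%.

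**Step 3: how likely a loss is.** Let q be the chance that a patient is lost in week 1 because of toxicity, and suppose enrolment continues until 32 are evaluable.

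- P(at least one lost) = 1 − (1 − q)^32
- Mean number lost = 32q/(1 − q)

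| Assumed q | P(at least one lost) | Mean lost |
|---|---|---|
| 1% | 1 − 0.99^32 = 0.275 | 0.32/0.99 = 0.32 |
| 2% | 1 − 0.98^32 = 0.476 | 0.64/0.98 = 0.65 |
| 5% | 1 − 0.95^32 = 0.806 | 1.60/0.95 = 1.68 |

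**The case against.** The strongest reply is that little is hidden. Every adverse event is recorded. Section 17.3 says "Any SAE must be reported to the IRB/PB as soon as possible but no later than 5 calendar days", and Section 17.3.2 says of liver events that "Protocol-specified AESI are to be reported in an expedited manner similar to Serious Adverse Events". Section 17.3.3 sends serious events and events of special interest to the drug's manufacturer. A reader might infer that early toxicity goes unrecorded or unreported; these sections show that it does not. The defect lies in the evaluated set alone.

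A reader might also infer that every patient stopped by toxicity in week 1 is lost. The hold-and-resume rules in Sections 9.3, 9.4.1 and 9.4.3 do not support that.

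The numbers affected may be small. The starting dose of 200 mg twice daily is below the 250 mg maximum tolerated dose that Section 3.8.2 gives for Caucasian patients (it equals the Japanese one). At q of 1% to 2%, fewer than one patient is lost on average, and the intervals above overlap widely. All of this stands, and it limits the expected size. It does not justify a rule that leaves out toxicity-related losses when they do occur.

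Finally, because Section 14.0 only tabulates toxicity and the protocol states no cumulative count that prompts review, a reader might infer that cumulative safety monitoring is missing. The documents do not show that. Section 16.3 describes a data and safety monitoring committee for phase I and II trials, has each protocol assessed for risk, and says "the monitoring procedures will be established at the time of protocol activation". Those procedures are not among the documents and may contain a trigger. Whether to add a numerical limit here is a trade-off for the investigators.

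**Conclusion.** The point holds for the toxicity evaluation, and the rule should be changed. As written, Section 12.0 biases the tolerability objective downward whenever a patient is lost in week 1 because of toxicity, and it conflicts with the wider scope of Sections 11.4, 12.3 and 17.3.1.

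On the illustrative base of 3/32, each of the first one or two such patients adds close to 3 percentage points to the true rate. Whether any will occur is unknown: the range of 28% to 81% rests on assumed first-week rates of 1% to 5%. The conclusion also assumes that the table in Section 14.0 uses the evaluable set of Section 12.0, which is the natural reading since no other set is defined. No claim is made here about the primary analysis, and the lack of a stated cumulative trigger is not part of the finding.

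**What to change.** In Section 12.0, restrict the one-week requirement and the replacement rule to response, and state that toxicity is evaluated in every patient who received any dose of Nintedanib, including those replaced. In Section 14.0, name that set as the denominator of the toxicity tables, and add that the number of patients replaced will be reported with the reason for each.

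The cost is about one sentence in each section. No new data are needed, because Sections 11.4 and 17.3.1 already collect these events. The toxicity denominator may then exceed 32, so tables should label the two sets. The 32 evaluable patients and the 6-of-32 PFS rule do not change.

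As an option only, Section 16.3 could cite the monitoring procedures set for this trial at activation under the institutional plan.

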# 12.2 Progression-free survival

The primary endpoint is to evaluate the 6-month progression free survival (PFS); hence patients with evaluable disease by RECIST are eligible for the trial. This is defined as the duration of time from start of treatment to time of progression or death from any cause. Patients who are taken off-study because of drug-related toxicity or other adverse event but who are alive and have stable or responding disease at the time of trial discontinuation will continue to follow per protocol, however, if they start another therapy, they will be considered as failure of therapy at that time and will be removed from protocol.

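### Patients who start nintedanib but cannot complete one week are dropped and replaced, so the earliest failures and toxicities leave the 32 patients on which the trial decides

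*Combined protocol and SAP*

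**What the plan says.** Section 12.0 sets one evaluability rule for the trial: "All patients who receive at least one week of Nintedanib will be evaluable for toxicity and response". Patients "unable to complete one week of therapy will not be evaluated for toxicity or response and will be replaced by a new patient". The rule makes no distinction between death, progression, toxicity, withdrawal and administrative reasons.

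Section 12.2 defines the primary endpoint, PFS: "This is defined as the duration of time from start of treatment to time of progression or death from any cause". It also keeps patients who come off because of toxicity with stable or responding disease in follow-up, and counts them as failures if they start another therapy.

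Section 14.0 plans an exact binomial single-stage design with 32 patients. On its terms "a 6 month PFS of 10% or less will be considered unacceptable while 28% or more will be considered promising", with "type I and II error rates of 10% each". The decision rule is: "If 6 or more patients are alive and progression free at 6 months, the regimen is declared promising". Section 14.0 names no analysis population. Section 4.3 plans to enrol 32 patients, with no allowance for replacements.

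On safety, Section 2.1 makes tolerability and the adverse event profile a secondary objective. Section 11.4 requires every adverse event after consent to be recorded, and Section 17.3.1 requires "All adverse events, serious and non-serious, occurring during the course of the clinical trial" to be collected and reported from consent onward.

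**The concern.** Whether a patient completes seven days of drug is known only after dosing has begun, and it depends on how the patient fares. A death on day 5 is a PFS event under Section 12.2, yet Section 12.0 removes that patient and puts another in the place. The 6-month PFS rate is then estimated among people who survived and tolerated the first week, and compared with a fixed 10% benchmark. In a single-arm trial no control group undergoes the same selection. To the extent that the removed patients are failures, the error favours the drug.

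The objective response rate is affected in the same way. For tolerability, the patients who react worst and soonest are the ones left out of the toxicity evaluation.

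**Working it through.** **Inputs.** From Section 14.0: n = 32, cut-off 6, null rate 10%, target rate 28%, type I and II error 10% each. The number of patients replaced, m, is not in the documents. I take m = 1 to 5 as an assumed range.

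**Step 1: the plan's own design.** With X binomial,

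- P(X ≥ 6 | n = 32, p = 0.10) = 0.0944
- P(X ≥ 6 | n = 32, p = 0.28) = 0.9186

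The design reproduces: type I error 9.4%, power 91.9%. The margin below the stated 10% is about 0.6 of a percentage point.

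**Step 2: replaced patients leave the 32.** If m patients are replaced, 32 + m are treated. Suppose the true rate among all treated is 10% and every replaced patient is a failure. All successes then fall among the 32 retained, whose rate is

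p = 0.10 × (32 + m) / 32

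and the chance of declaring the regimen promising is P(X ≥ 6 | 32, p).

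| Replaced (m) | Treated | Rate among the 32 | Type I error |
|---|---|---|---|
| 0 | 32 | 10.0% | 9.4% |
| 1 | 33 | 10.3% | 10.6% |
| 2 | 34 | 10.6% | 11.8% |
| 3 | 35 | 10.9% | 13.1% |
| 4 | 36 | 11.3% | 14.4% |
| 5 | 37 | 11.6% | 15.8% |

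The same effect can be expressed through a first-week drop-out proportion d, with p = 0.10 / (1 − d). The type I error is 10.6% at d = 3%, 11.4% at d = 5% and 13.8% at d = 10%.

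**Step 3: the other reading.** Suppose replaced patients were still counted for PFS. The denominator then exceeds 32 while the cut-off stays at 6:

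- P(X ≥ 6 | 33, 0.10) = 0.106
- P(X ≥ 6 | 34, 0.10) = 0.119

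To bring the error back under 10%, the cut-off must rise to 7 after a single replacement. At 7 of 33 the type I error is 4.2% and power 85.7%. So the rule as written exceeds 10% on either reading once one patient is replaced.

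**Step 4: toxicity.** If two patients stop in week 1 for severe toxicity and are replaced, the rate among treated patients is 2/34 = 5.9%. Among the evaluable patients of Section 12.0, the same two events appear as 0 of 32.

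**The case against.** The strongest objection is that Section 12.0 speaks of toxicity and response and does not name PFS. Section 14.0 sends the reader to Section 12.2 for PFS, and that section has its own rules and no one-week condition. This is a real ambiguity, but it does not rescue the plan. Section 12.0 introduces the whole outcome section, and a replaced patient no longer fills one of the 32 places. If PFS did retain such patients, the cut-off of 6 would no longer be calibrated (step 3).

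A second objection is that no safety data are lost. That is right as far as records go: Sections 11.4 and 17.3.1 still require every adverse event to be recorded and reported, and Section 14.0 does not state the denominator of its toxicity table. The conflict concerns the toxicity evaluation, from which Section 12.0 explicitly removes these patients.

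A third objection is size. Eligibility requires a life expectancy of at least 6 months and KPS of at least 70%, and the first scheduled scan is at eight weeks, so first-week deaths and documented progressions should be few. Five replacements would mean 5/37 = 13.5% of treated patients stopping within a week. A patient who stops for toxicity may also still be progression-free at 6 months, so treating every replaced patient as a failure is the worst case. All of this stands, and the probable effect is modest. It still takes only one replaced failure to pass the stated 10%.

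Finally, counting everyone could cost power if 28% was meant to describe evaluable patients only; the documents do not say. That also stands, and its size is given under the fix.

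**Conclusion.** The concern holds. Section 12.0 excludes and replaces patients on the basis of what happens after dosing. That contradicts the PFS definition in Section 12.2 and undercuts the tolerability objective. The type I error rises from 9.4% to between 10.6% (one replaced) and 15.8% (five replaced).

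These figures assume that the true 6-month PFS among all treated patients is 10% and that every replaced patient is a failure. They are upper values for each count, and the count itself is unknown. One or two replacements would shift the error only slightly. The correction should nevertheless be made, because the rule bears on the primary decision, the response rate and the toxicity summary together, and removing it needs only a change of wording.

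**What to change.** Rewrite the evaluability rule in Section 12.0, and name the analysis set in Section 14.0, as follows:

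- Every patient who takes at least one dose counts among the 32, in the primary analysis, the response analysis and the toxicity table.
- A patient who stops in week 1 is followed under Section 12.2. That patient is counted as not progression-free at 6 months unless follow-up documents otherwise, and as a non-responder unless a response is documented.
- Only registered patients who never take a dose may be replaced.

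Keep n = 32 and the cut-off of 6. With the first 32 treated patients counted and 28% read as the rate among all treated, the design has 9.4% type I error and 91.9% power.

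**Cost.** The change needs no extra patients or procedures, and the reported rates may be slightly less favourable. If 28% was meant for evaluable patients only and week-1 stops are all failures, the rate among the 32 with m stops is 0.28 × (32 − m) / 32. Power is then 90.1% with one stop, 88.1% with two, 85.8% with three and 80.2% with five, so from two stops onward it falls below 90%. Section 14.0 should therefore state that 10% and 28% refer to all treated patients.
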